### **5.3 Lifestyle Considerations**

All study participants will be instructed not to donate blood or blood products or sperm or eggs during the study (including the run-in period) and for at least 18 weeks after the last dose of the IP.

Participants who are current smokers or who vape are not excluded.

### **5.4 Replacements and Screen Failures**

A screen failure occurs when a participant who has consented to participate in the clinical study is not subsequently assigned to the IP. A minimal set of screen failure information is required to ensure transparent reporting of screen failure participants to meet the Consolidated Standards of Reporting Trials publishing requirements and to respond to queries from regulatory agencies. Minimal information includes demography, screen failure details, eligibility criteria, and any serious AEs (SAEs).

Individuals who are to be rescreened must first sign a new ICF, consent to the rescreening, and attest to their understanding of the study. Such individuals will be assigned a new participant number.

An individual may be rescreened only once. An individual who does not meet the criteria for participation in this study may be rescreened if the reason for screen failure has resolved and if the sponsor has approved the rescreening.

When a participant is rescreened, all the screening tests and procedures must be repeated. An additional chest x-ray is not needed, if the previous one has been done within 12 months from rescreening and the report is available.

## **6 Study Treatments**

Study treatments intended to be administered in this study to all participants includes the IP (lebrikizumab and PBO) and mometasone furoate as a required background medication. The use of concomitant medications and rescue medications is described in [Section 6.10.2](#) and [Section 6.10.3](#), respectively.

## 6.1 Study Treatments Administered

This study involves administration of IP (lebrikizumab and or PBO) and background medication (mometasone furoate), as shown in [Table 6-1](#).

**Table 6-1 Study Treatments Administered**

Study Treatment	Lebrikizumab	Placebo	Mometasone Furoate
Study Treatment Name	LY3650150	Placebo to match	INCS
Dose Formulation	PFS-NSD to deliver 2.0 mL	PFS-NSD to deliver 2.0 mL	Metered spray
Unit Dose Strength(s)	250 mg, 125 mg/mL	Matched PBO, lacking lebrikizumab	50 µg per spray
Dosage Level(s)	500 mg (2 PFS-NSD) loading dose	2 PFS-NSD loading dose	200 µg (2 sprays in each nostril), BID
	250 mg (1 PFS-NSD) induction and maintenance dose	1 PFS-NSD induction and maintenance dose	
Route of Administration	Subcutaneous injection	Subcutaneous injection	Nasal spray
Authorized as Defined by EU CTR	Not authorized	Not authorized	Authorized and used according to authorization

Note: Placebo study treatment is only applicable for adult participants.

Abbreviations: BID = twice daily; EU CTR = European Union Clinical Trials Register; INCS = intranasal corticosteroid; PBO = placebo; PFS-NSD = prefilled syringe with needle safety device.

The schedules for administration of blinded lebrikizumab Q2W/Q4W arm, lebrikizumab Q2W/Q8W arm, and PBO arm are presented in [Table 6-2](#) and [Table 6-3](#)). Study sites will dispense study treatment for administration at home according to the SoA ([Table 1-1](#)). Study treatments will be supplied in accordance with current Good Manufacturing Practice. IP will be labeled as appropriate for country requirements.

Background medications will be dispensed to all participants for use throughout the study, according to the SoA ([Table 1-1](#)). Further details on dosing of background interventions are presented in [Section 6.10.2.2](#). Participants who are not comfortable self-administering IP away from the study site may come to the study site for administration according to the “away” administration schedule. Refer to [Section 4.1](#) for randomization and treatment assignments.

**Table 6-2 Loading Dose and Induction Period Dosing Schedule**

Week	W0 Clinic	W2 Clinic	W4 Clinic	W6 Clinic	W8 Clinic	W10 Away	W12 Away	W14 Away	W16 Clinic	W18 Away	W20 Away	W22 Away
Visit	V3	V4	V5	V6	V7	-	-	-	V8	-	-	-
Arm												
Lebrikizumab Q2W/Q4W	500 mg (2 injections)	500 mg (2 injections)	250 mg	250 mg	250 mg	250 mg	250 mg	250 mg	250 mg	250 mg	250 mg	250 mg
Lebrikizumab Q2W/Q8W	500 mg (2 injections)	500 mg (2 injections)	250 mg	250 mg	250 mg	250 mg	250 mg	250 mg	250 mg	250 mg	250 mg	250 mg
PBO	2 PBO	2 PBO	1 PBO	1 PBO	1 PBO	1 PBO	1 PBO	1 PBO	1 PBO	1 PBO	1 PBO	1 PBO

Abbreviations: PBO = placebo; Q2W = every 2 weeks; Q4W = every 4 weeks; Q8W = every 8 weeks; W = week (as in W0; Week 0).

Note: Participants who are not comfortable self-administering IP away from the study site may come to the clinic for administration according to the “away” administration schedule. Enrollment of adolescents will be open-label, with all adolescents assigned to the lebrikizumab Q2W/Q4W treatment arm.

**Table 6-3 Maintenance Period Dosing Schedule**

Week	W24 Clinic	W28 Away	W32 Away	W36 Away	W40 Clinic	W44 Away	W48 Away	W52 Away	W56 Clinic
Visit	V9	-	-	-	V10	-	-	-	V11
Arm									
Lebrikizumab Q2W/Q4W	250 mg	250 mg	250 mg	250 mg	250 mg	250 mg	250 mg	250 mg	No dose
Lebrikizumab Q2W/Q8W	250 mg	1 PBO	250 mg	1 PBO	250mg	1 PBO	250 mg	1 PBO	No dose
PBO	1 PBO	1 PBO	1 PBO	1 PBO	1 PBO	1 PBO	1 PBO	1 PBO	No dose

Abbreviations: PBO = placebo; Q2W = every 2 weeks; Q4W = every 4 weeks; Q8W = every 8 weeks; W = week (as in W0; Week 0).

Note: Participants who are not comfortable self-administering IP away from the study site may come to the clinic for administration according to the “away” administration schedule. Enrollment of adolescents will be open-label, with all adolescents assigned to the lebrikizumab Q2W/Q4W treatment arm.

### **6.1.1 Instructions for Administration at the Study Site**

The IP will be administered under medical supervision by the investigator or designee at scheduled study site (clinic) visits according to the SoA ([Table 1-1](#)), [Table 6-2](#), [Table 6-3](#), and instructions in the study reference manual. There must be at least 7 days between IP dosing. The dose of IP and study participant identification will be confirmed prior to dispensing IP. Study site staff may also administer the IP to participants who are not comfortable self-administering IP away from the study site and come to the study site for administration according to the “away” administration schedule.

Study sites will provide proper instruction on correct nasal spray technique for mometasone furoate.

### **6.1.2 Instructions for Administration Away From the Study Site**

Study site staff will instruct participants in the administration of the IP and background intervention away from the study site according to [Table 6-2](#) and [Table 6-3](#) and instructions in the study reference manual. There must be at least 7 days between IP dosing. The participant or caregiver will be trained prior to beginning "away" injections and will be provided with instructions for use to take home. Participants will record away administration of the IP and background medication in an eDiary ([Section 10.1.1](#)).

Beginning at run-in and through Week 56, all participants will be required to use mometasone furoate 50 µg/actuation 2 sprays in each nostril twice daily (BID; total daily dose of 400 µg) ([Section 6.10.2.2](#)). Participants may continue on mometasone in the SFU period at the discretion of the investigator.

## **6.2 Preparation, Handling, Storage, and Accountability**

The study reference manual provides general instructions for the handling and storage of the IP, as well as the study site’s responsibility and accountability for the administered products. For storage information for lebrikizumab and PBO, refer to the IP label.

The investigator or designee must confirm that appropriate temperature conditions have been maintained during transit for all IP received and that any discrepancies are reported and resolved before use of the IP.

Only participants enrolled in the study may receive study treatment and only personnel authorized by an investigator or by the sponsor may supply or administer study treatment.

All study treatment must be stored in a secure, environmentally controlled, and monitored (manual or automated) area in accordance with the labeled storage conditions with access limited to the investigator and authorized site staff (unless the study treatment will be administered at home by the participant or caregiver). At home storage instructions are provided in the participants' instructions for use.

In addition, the investigator is responsible for keeping accurate records of when and how much IP is dispensed and used by each participant in the study. Only participants enrolled in the study may receive the IP and only authorized site staff may supply or administer the IP. Reasons for departure from the expected dispensing regimen must also be recorded in study source documents. At the completion of the study, to satisfy regulatory requirements regarding IP accountability, all IP will be reconciled and retained or destroyed according to applicable regulations.

Unused IP must not be discarded or used for any purpose other than for administration to participants enrolled in this clinical study. The IP that is dispensed to a participant, but not administered by the participant, must be returned to the study site for drug accountability.

Further guidance and information for the final disposition of unused IP are provided in the study reference manual.

The investigator has the responsibility for keeping accurate records of background medication (mometasone furoate) dispensed to participants and corresponding to recordkeeping responsibility.

The sponsor will be responsible for delivering IP to study sites.

### **6.3 Assignment to Investigational Product**

All participants will be centrally assigned to IP using an interactive web response system (IWRS). Before the study is initiated, the log-in information and directions for using the IWRS will be provided to each study site.

Assignment for adult participants will be randomized and stratified by asthma and/or AERD versus no asthma/no AERD, prior NP surgery versus no prior NP surgery, and geographic region (North America, Europe, rest of the world). All eligible adolescents will be assigned to open-label lebrikizumab Q2W/Q4W treatment.

### **6.3.1 Other Supplies**

An eDiary ([Section 10.1.1](#)) may be provided to each study site for each participant, and electronic tablets will be provided for capture of patient-reported outcome (PRO) data at study site visits.

The sponsor or the study site will supply background medication (mometasone furoate).

## **6.4 Blinding**

This is a double-blind study for the adult cohort of participants. The sponsor or designee(s), the investigator, study site staff, and the participant will be blinded to treatment assignment. The integrity of the clinical study will be maintained by observing the treatment blind.

Adult participants assigned to the Q2W/Q8W lebrikizumab arm will receive PBO on alternate scheduled dosing days during the maintenance period to maintain blinding ([Table 6-3](#)). Adult participants assigned to the PBO arm will receive Q4W injections during the maintenance period ([Table 6-3](#)).

Adolescent participants will not be blinded to treatment as they will be assigned to open-label lebrikizumab Q2W/Q4W.

### **6.4.1 Breaking the Blind**

The IWRS will be programmed with blind-breaking instructions. In case of an emergency, the investigator has the sole responsibility for determining if unblinding of a participant's IP assignment is warranted. Participant safety must always be the first consideration in making such a determination. If the investigator decides that unblinding is warranted, it is the responsibility of the investigator to promptly document the decision and rationale and notify the sponsor or designee(s) within 24 hours. The date on which the code was broken together with the identity of the person responsible must also be documented.

If an investigator, study site staff performing assessments, or participant is unblinded, the participant must be discontinued from the study. In cases where there are ethical reasons to have the participant remain in the study, the investigator must obtain specific approval from a sponsor clinical research physician for the participant to continue in the study.

## **6.5 Compliance With Planned Study Treatment Administration**

Details on administration of the study treatment in the study site are in [Section 6.1.1](#). When participants are dosed at the study site, they will receive the study treatment directly from the investigator or designee under medical supervision. The date and time of each dose administered in the clinic will be recorded in the source documents and in the electronic case report form (eCRF). The dose of study treatment and study participant identification will be confirmed at the time of dosing by a member of the site staff other than the person administering the study treatment.

Details on self-administration away from the study site are in [Section 6.1.2](#). When participants self-administer study treatment away from the study site, compliance with study treatments will be assessed at each visit. Compliance will be assessed by review of the eDiary and counting of returned IP and will be documented in the source documents and in the eCRF. Deviation(s) from the prescribed dosage regimen should be recorded. The participants will record their dosing of study treatment (IP and background) in their eDiaries ([Section 10.1.1](#)).

A record of the study treatment dispensed to and administered by each participant or caregiver must be maintained and reconciled with study treatment and compliance records. A participant will be considered compliant with the IP dosing regimen if the participant receives 75% of the expected number of injections while enrolled in the study. Compliance with protocol-specified background medication will be required and monitored for each participant.

## **6.6 Dose Modification**

Dose modifications of the IP are not allowed, except for background therapy as noted in [Section 6.10.2.2](#) in this study. Details are specified in the study reference manual.

## **6.7 Continued Access to Investigational Product After the End of the Study**

No continued access to IP is planned after the end of this study.

## **6.8 Management of Overdose**

An overdose is any dose of IP given to a participant or taken by a participant, accidentally or intentionally, that exceeds the dose specified in the protocol. In case of suspected overdose, hematology, clinical chemistry, vital signs, and oxygen saturation should be monitored and supportive care provided as necessary.

In the event of an overdose, the investigator should:

- Contact the medical monitor immediately, and
- Closely monitor the participant for any AE/SAE and laboratory abnormalities.

Whenever possible and considering the safety of the participant, decisions regarding dose interruptions should be made by the investigator in consultation with the medical monitor based on the clinical evaluation of the participant.

## **6.9 Management of Medication Errors**

Medication errors at a study site will be managed by the investigator or their designated qualified medical professional.

To help identify medication errors away from the study site, study site staff will provide instructions for correct use of IPs (including written instructions) and for reporting medication errors or by contacting the study site in case of emergency (eg, a nonparticipant uses an IP).

## **6.10 Prior, Concomitant, and Rescue Medications and Therapies**

Any medication (including vaccines and over-the-counter or prescription medicines, recreational drugs, vitamins, and/or herbal supplements) that the participant is taking at the time of screening or subsequently during the study enrollment or receives during the study must be recorded, including the following:

- Identity (specific to product name if a combination drug product), spelled correctly.
- Reason for use.
- Dates of administration, including start and end dates.
- Dosage information, including dose, frequency, and route of administration.

The medical monitor should be contacted if there are any questions regarding prior or concomitant therapy.

### **6.10.1 Prior Medications**

A history of prior medications and relevant therapies should be collected as part of the medical history taken at screening. Restrictions on prior medications and therapies are found in the exclusion criteria ([Section 5.2](#)).

### **6.10.2 Concomitant Medications**

All medications (including vaccines and over-the-counter drugs or prescription medicines, herbal supplements, vitamins, and antacids) taken/used at screening and throughout the study must be recorded. The investigator is expected to examine the acceptability of all concomitant medications, topical preparations, and dietary supplements taken by the study participants.

The use of concomitant medications for other medical conditions (eg, hypertension, diabetes, acute infections) is permitted during this study ([Section 6.10.2.2](#)). Inhaled corticosteroids (ICS) and combination with long-acting bronchodilators to control asthma are permitted if on stable doses for 3 months prior to screening ([Section 5.1](#)).

Medication entries should be specific to product name (if a combination drug product) and spelled correctly.

Information on the dose, unit, frequency, route of administration, start date, discontinuation date, and indication will be recorded.

The use of any concomitant medication must relate to an AE listed on the AE page in the eCRF or the participant's medical history unless it is a supplement or used as preventive care.

### **6.10.2.1 Prohibited Concomitant Medications**

In addition to the medications listed in [Section 5.2](#), the following will be prohibited during the study:

- Daily aspirin for treatment of AERD (aspirin is allowed as needed for pain relief or other indications).
- Intranasal antihistamines or combination intranasal corticosteroid antihistamines (eg, azelastine, olopatadine/mometasone furoate).
- Any biologic not approved for CRSwNP according to local regulatory authorization.
- Systemic antimicrobials >10 days.
- Nasal saline lavage with antibiotics and/or nasal saline lavage with corticosteroids (>10 days).
- Any systemic immunosuppressive treatment.
- Allergy immunotherapy (SCIT/SLIT), except if initiated more than 6 months prior to screening (Visit 1) and the dose is stable 3 months prior to screening (Visit 1) with no change in dose during the study.
- Use of INCS (other than mometasone furoate).
- Long-term course (>7 days) of SCS for any indications.

- Use of SCS between screening (Visit 1) and baseline (Visit 3) (screening and run-in period).
- Fluticasone propionate.
- Oral decongestants for any length of time to treat CRSwNP or oral decongestants >5 days to treat an acute adverse event.
- Intranasal decongestants, except as single use for nasal endoscopy.
- Leukotriene receptor antagonists.
- Live or live attenuated vaccines.

Participants who take any prohibited medications must discontinue from IP, but can remain in the study, unless the investigator decides to withdraw the participants from the study.

### **6.10.2.2 Allowed Medications**

Concomitant medications participants can take during the study are presented in [Section 6.10.2](#). Participants will be allowed to use the following medications:

- INCS, mometasone furoate 50 µg/actuation 2 sprays in each nostril BID (total daily dose of 400 µg) required by all participants during run-in period and through Week 56, if participants are unable to tolerate BID dosing or a specific regulatory requirement preventing use of this dose, participants can stay on a lower dose of 200 µg mometasone furoate (2 sprays/nostril once a day). Use of mometasone furoate at a higher dose is not allowed.
- Stable dose of ICS ([Section 6.10.2](#)).
- Nasal saline lavage, except on the day of the visit.
- Nasal saline lavage with antibiotics and/or nasal saline lavage with corticosteroids (≤10 days), except on the day of the visit.
- Single topical decongestants and single topical anesthetic administered for the purpose of nasal endoscopy.

- Local anesthetics (for example, EMLA cream) consistent with local prescribing information are permitted during the study visit to ease discomfort associated with venipunctures.
- Systemic antimicrobials  $\leq 10$  days.
- Stable doses of ICS, short-acting beta agonist, ICS/long-acting beta2 agonists, and long-acting muscarinic antagonists.
- Systemic antihistamines.
- Oral decongestants  $\leq 5$  days used to treat any acute adverse event other than CRSwNP.
- Non-live vaccines.
- Stable dose allergy immunotherapy (SCIT/SLIT) initiated  $>6$  months prior to screening (Visit 1).
- Stable dose methylxanthines (eg, theophylline, aminophyllines).
- Short-term course ( $\leq 7$  days) of SCS for any indications ([Section 6.10.3](#)).

### **6.10.3 Rescue Medication and Surgery for CRSwNP**

Investigators should conduct efficacy (PROs and endoscopy) and safety assessments before starting any rescue medication. An unscheduled visit should be used for this purpose if necessary.

During the induction and maintenance, if the participant experiences worsening signs and symptoms that require medical intervention based on clinical evaluation by the investigator, the investigator may consider the following rescue treatment.

- Nasal saline lavage with antibiotics and/or nasal saline lavage with corticosteroids.
- SCS.
- Approved biologic for CRSwNP based on local regulatory approval.
- Need for surgery for NP.

Participants who receive rescue medication or plan for NP surgery must comply with the following:

- Participants receiving nasal saline lavage with antibiotics and/or nasal saline lavage with corticosteroids ( $\leq 10$  days) during the study will continue on IP, unless the investigator decides to discontinue IP.
- Participants receiving nasal saline lavage with antibiotics and/or nasal saline lavage with corticosteroids ( $> 10$  days) during the study will discontinue IP, but can remain in the study, unless the investigator decides to withdraw the participant from the study.
- Participants receiving short-term SCS ( $\leq 7$  days) rescue treatment during the study will continue on IP unless the investigator decides to discontinue IP.
- Participants receiving long-term SCS ( $> 7$  days) rescue treatment during the study will discontinue IP, but can remain in the study, unless the investigator decides to withdraw the participants from the study.
- Participants who receive an approved biologic for CRSwNP as a rescue treatment will discontinue IP but can remain in the study, unless the investigator decides to withdraw the participant from the study.
- Participants who need surgery for NP as a rescue treatment will discontinue IP, but can remain in the study, unless the investigator decides to withdraw the participant from the study. These participants may continue IP until the date of surgery.

## **7 Discontinuation From Investigational Product and Participant Withdrawal from the Study**

### **7.1 Discontinuation of Investigational Product**

Participants may discontinue from the IP at any time and for any reason without prejudice to their future medical care by the investigator or at the study site. Every effort should be made to keep participants in the study. Participants may continue the study even if discontinuing IP.

The reasons for participants discontinuing the IP, based on the judgment of the investigator and/or the sponsor, will be recorded. At the discretion of the investigator, a participant may be discontinued from the IP for any of the following reasons:

- The participant discontinues IP for any reason, including the following:
  - Does not tolerate the IP
  - Does not perceive a benefit from the IP
  - Prefers an alternative treatment
  - Other reason (to be specified in the eCRF)
- The participant experiences a serious or intolerable AE(s) that in the investigator's opinion required discontinuation from IP.
- The participant has laboratory safety results that revealed clinically significant hematologic or biochemical changes from the baseline values.
- In the opinion of the investigator, the participant should permanently discontinue the IP for safety reasons.
- The participant develops any new medical condition or contraindication that would render continued administration of the IP unsafe in the investigator's opinion.
- The participant has an intercurrent illness that would, in the opinion of the investigator, affect assessments of clinical status to a significant degree.

- Other reasons (to be specified in the eCRF).
- Participants who take any prohibited concomitant medication or rescue intervention listed in [Section 6.10.2.1](#) and [Section 6.10.3](#) must discontinue IP but can continue in the study.

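### Section 7.1 orders study drug stopped after any rescue listed in 6.10.3, while 6.10.3 keeps participants on it after short steroid courses or short medicated lavage

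*Protocol*

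**What the plan says.** **Section 7.1, last bullet.** Those covered are "Participants who take any prohibited concomitant medication or rescue intervention listed in" Sections 6.10.2.1 and 6.10.3, and they "must discontinue IP but can continue in the study". The bullet has no duration limit. It closes a list that opens with discretionary wording: "At the discretion of the investigator, a participant may be discontinued from the IP for any of the following reasons".

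**Section 6.10.3.** The rescue options are medicated nasal lavage (antibiotics and/or corticosteroids), SCS, an approved biologic, and need for nasal polyp (NP) surgery. Instructions then follow by type and duration. Participants on SCS for 7 days or less as "rescue treatment during the study will continue on IP unless the investigator decides to discontinue IP". Those on medicated lavage for 10 days or less "during the study will continue on IP, unless the investigator decides to discontinue IP". IP must stop for SCS beyond 7 days, lavage beyond 10 days, an approved biologic, or NP surgery, and in the surgical case dosing may go on until the day of surgery.

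**Sections 6.10.2.2 and 6.10.2.1.** The allowed list contains SCS courses of up to 7 days and "nasal saline lavage with corticosteroids (≤10 days), except on the day of the visit". After baseline, the prohibited list bars SCS only as "Long-term course (>7 days) of SCS for any indications", bars corticosteroid lavage only beyond 10 days, and ties stopping IP to prohibited medications.

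**The concern.** For two common forms of rescue, the protocol gives a site opposite instructions on whether to give the next injection. Section 7.1 is where a site would look for the rules on stopping IP, and its bullet is phrased as an obligation. A site that obeys it withdraws study drug from a participant whose rescue the protocol expressly permits.

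In a lebrikizumab participant this removes active treatment that was meant to continue. The primary estimand uses treatment policy for IP discontinuation, so the off-drug data stay in the comparison. Placebo participants lose no active drug, so any dilution falls on the lebrikizumab side. It would also inflate the count of IP discontinuations (ICE1 in Table 9-1). Sites that rely on different sections would dose their participants differently.

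**Working it through.** **1. The rules side by side**

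| Rescue | 7.1, read literally | 6.10.3 | Agree? |
|---|---|---|---|
| SCS ≤7 days | stop IP | continue by default | no |
| Medicated lavage ≤10 days | stop IP | continue by default | no |
| SCS >7 days | stop IP | stop IP | yes |
| Medicated lavage >10 days | stop IP | stop IP | yes |
| Approved biologic | stop IP | stop IP | yes |
| NP surgery performed | stop IP | stop IP, dosing allowed until surgery | yes, though only 6.10.3 fixes the date |

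No other section adds a duration limit to the 7.1 bullet. Table 9-1 lists IP discontinuation (ICE1) and short-term SCS (ICE2) as separate events. Under literal 7.1, every short SCS rescue course would also produce an ICE1. That suggests 6.10.3 is the intended rule.

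**2. Active injections lost per affected participant (Tables 6-2 and 6-3)**

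- Induction, both lebrikizumab arms: Week 0 (2) + Week 2 (2) + Weeks 4 to 22 every 2 weeks (10) = 14.
- Maintenance: Q4W, Weeks 24 to 52 = 8; Q8W, Weeks 24, 32, 40 and 48 = 4.
- Totals: 14 + 8 = 22 and 14 + 4 = 18.

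Lost = total minus given. The stop date is an assumption, so a range is shown.

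| Stop after | Given | Lost, Q2W/Q4W | Lost, Q2W/Q8W | Induction doses lost |
|---|---|---|---|---|
| Week 0 | 2 | 20 of 22 (90.9%) | 16 of 18 (88.9%) | 12 of 14 |
| Week 8 | 2+2+1+1+1 = 7 | 15 of 22 (68.2%) | 11 of 18 (61.1%) | 7 of 14 |
| Week 22 | 14 | 8 of 22 (36.4%) | 4 of 18 (22.2%) | 0 |
| Last active dose | all | 0 | 0 | 0 |

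**3. How many participants**

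The protocol gives no rate for short SCS or short lavage. Section 9.3 assumes 10% of lebrikizumab participants have a rescue event over the treatment period (SCS, approved biologic or planned surgery), and Section 9.5.4 counts any SCS use as an event. If that rate holds, short-SCS participants number between 0 and 0.10 × 340 = 34. Lavage lies outside this ceiling.

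**4. Could this threaten the co-primary result?**

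Inputs from Section 9.3: nasal congestion score (NCS) difference 0.62, SD 1.0; nasal polyp score (NPS) difference 1.48, SD 2.1; two-sided alpha 0.01; 20% dropout. Normal approximation: power = Φ(difference/SE − 2.576), with SE = SD × √(1/n₁ + 1/n₂).

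- *Plan's figure*, 170 × 0.8 = 136 per arm. NCS: SE 0.1213, z = 5.11, power 99.4%. NPS: SE 0.2547, z = 5.81, power 99.9%. Product about 99.4%, in line with the stated 99%.
- *Extreme case.* Suppose 10% of lebrikizumab participants lose all benefit by Week 24. Section 9.5.1 pools the two lebrikizumab arms for induction, giving 136 against 340 × 0.8 = 272. NCS: 0.9 × 0.62 = 0.558, SE 0.1050, z = 5.31, power Φ(2.74) = 99.7%. NPS: 0.9 × 1.48 = 1.332, SE 0.2205, z = 6.04, power Φ(3.46), above 99.9%.

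Power stays above 99% for each endpoint.

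**The case against.** The strongest reply is that the conflict resolves itself. The 7.1 bullet lists no rescues of its own, so a site must open 6.10.3, where it finds mandatory, duration-specific instructions. The adjective *prohibited* can also be read as governing rescue interventions too, and on that reading the conflict shrinks, because the short courses are not prohibited. The 6.10.3 instruction is itself a default that leaves the investigator free to stop IP, and the 7.1 list opens with discretionary language. Treatment policy applies to both ICE1 and ICE2, participants stay in the study under either section, and the extreme power check shows no danger to the main result. On this view it is an editorial slip.

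Much of that stands. Section 6.10.3 is the more specific text and very likely the intent, data handling is unaffected, and how many sites would follow 7.1 is unknown. Three things do not go away:

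- That 6.10.3 is also mandatory makes this two binding rules in conflict; it does not say which prevails.
- The milder reading fits poorly. Section 6.10.3 labels no rescue as prohibited, 6.10.2.1 already requires stopping for prohibited medication, and NP surgery, a 6.10.3 rescue, is not on the prohibited list.
- Discretion to stop under 6.10.3 differs from an obligation to stop under 7.1. An obligation placed in a discretionary list leaves 7.1 unclear even on its own.

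**Conclusion.** The concern holds. As written, 7.1 and 6.10.3 give opposite IP instructions for SCS of up to 7 days and medicated lavage of up to 10 days. No conflict is claimed for the longer courses, approved biologics or performed NP surgery.

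The harm is avoidable loss of active exposure and inconsistent dosing between sites. Per affected lebrikizumab participant it runs from 0 to 20 injections depending on when the stop occurs. The ceiling of about 34 participants for SCS rests on the 10% planning rate and on every rescue event being a short SCS course at a site that follows 7.1. The estimand, the Type I error control and the analysis are untouched. The point merits correction because it is a dosing rule in a trial still to be conducted consistently across sites, not because the trial's conclusion is at risk.

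**What to change.** Rewrite the last bullet of 7.1 so that stopping IP is required only for:

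- medications prohibited in 6.10.2.1; and
- rescues for which 6.10.3 requires it: SCS beyond 7 days, lavage with antibiotics and/or corticosteroids beyond 10 days, an approved biologic, and NP surgery from the date of surgery.

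Move it out of the discretionary list and send sites a short clarification that short SCS and short lavage courses do not by themselves end dosing. ICE1 and ICE2 in Table 9-1 need no change for this.

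The cost is a one-bullet correction or clarification letter and a site memo, with no added participants, procedures or analyses.
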